4.3 JUSTIFICATION FOR DOSE

Transcranial alternating current stimulation (tACS) is an extremely safe non-invasive stimulation paradigm without a single serious adverse event directly related to stimulation. The same tACS method has been used during performance of a task with intermittent resting-state EEG in our previous approved UNC IRB protocol 18-0003 (NCT03800030) that was overseen by [name]. A similar experimental design using a single session with reward-based

decision-making tasks and tACS in participants with major depressive disorder (MDD) was approved in our previous UNC IRB protocol 16-1911 (NCT03449979) that was overseen by [name]. Transcranial Alternating Current Stimulation (tACS) applies a weak electric current to the scalp and all previous studies (approximately 15 to date) performed in the Carolina Centers for Neuroimaging and Neuroinformatics at UNC IRB. Thus, no direct FDA oversight is required and no investigational device application filing is required. Further conversations with the regulatory core of the UNC CTSA and the director of the Office of Human Research Ethics that administers the UNC IRB over the years have consistently confirmed this classification.

tACS will be delivered using a cross-frequency stimulation waveform delta-beta (3-20Hz), a control frequency of theta-gamma (5-50Hz), or sham in which stimulation is delivered in either delta-beta or theta-gamma for 10 seconds and then returns to baseline (Figure 1). These waveforms were designed based on our previous experiment that observed these brain activity patterns in a reward-based decision-making task in participants with MDD. The stimulation amplitude delivered is standard for tACS studies (Ahn, Mellin et al. 2018, Alexander, Alagapan et al. 2019) – stimulation peaks at 1 mA during the peak of the high-frequency component for target electrodes (see Y-axis of Figure 2). The high frequency component consists of 3.5 cycles of a sine-wave of the high frequency that is centered at 90 degrees of each cycle of the low-frequency component. Stimulation peaks at 2 mA zero-to-peak for the return electrode, but the electrode size is 35 cm² for the return electrode and 20.25 cm² for each of the target electrodes. Thus, the current density is comparable between the two: 0.057 mA/cm² for the return electrode and 0.049 mA/cm² for the target electrodes.

4.4 END OF STUDY DEFINITION

The end of this study is defined as when the last participant completes the study (i.e., the 48th participant to complete their final session).

5. STUDY POPULATION

5.1 INCLUSION CRITERIA

In order to be eligible to participate in this study, a participant must meet all of the following criteria:

- Between the ages of 18 and 65
- Able to provide informed consent
- Have normal to corrected vision
- Willing to comply with all study procedures and be available for the duration of the study
- Speak and understand English
- Low suicide risk as determined by both the Mini International Neuropsychiatric Interview (MINI) for the DSM-5 (assessment of suicidal ideation by the Columbia Suicide Severity Rating Scale (C-SSRS; Ghahramani et al., 2015)) and by the Hamilton Depression Rating Scale (HAM-D; less than 3 for the suicidality item).
- Negative pregnancy test for female participants
- PHQ-8 greater than or equal to 8 prior to the first session
- PHQ-9 greater than or equal to 10 at the start of the first session
- A diagnosis of major depressive disorder on the MINI

5.2 EXCLUSION CRITERIA

A potential participant who meets any of the following criteria will be excluded from participation in the study:

- ADHD (currently under treatment)
- Neurological disorders and conditions, including, but not limited to:
 - History of epilepsy
 - Seizures (except childhood febrile seizures)
 - Dementia
 - History of stroke
 - Parkinson's disease
 - Multiple sclerosis
 - Cerebral aneurysm
 - Brain tumors
- Medical or neurological illness or treatment for a medical disorder that could interfere with study participation (e.g., unstable cardiac disease, HIV/AIDS, malignancy, liver or renal impairment)
- Prior brain surgery
- Any brain devices/implants, including cochlear implants and aneurysm clips
- History of current traumatic brain injury
- (For females) Pregnant or breast feeding
- Anything that, in the opinion of the investigator, would place the participant at increased risk or preclude the participant's full compliance with or completion of the study
- DSM-V diagnosis of present moderate or severe substance use disorder or alcohol use disorder, and past severe substance use disorder or alcohol use disorder, or psychotic disorder within the last 12 months
- Not taking medications for ADHD or benzodiazepines as these medications often produce specific EEG activity that may disrupt our interpretation of the findings
- If major depressive disorder is experienced in episode, the participant must currently be within a depressive episode.
- Contraindications for MRI: ferrous metal inside the body, jewelry must be removable, pacemaker or cochlear implant.

5.3 LIFESTYLE CONSIDERATIONS

None.

5.4 SCREEN FAILURES

In the design of this study, initial phone screening procedures should identify the majority of participants who could potentially become screen failures if consented to participate in the clinical trial. However, the phone screening process does not necessarily account for all exclusion criteria. After the phone screening, each participant is provided with a link to complete two online assessments via REDCap: the Patient Health Questionnaire (PHQ-8, without the suicide question) and the Snaith-Hamilton Pleasure Scale (SHAPS). Participants must have a PHQ-8 greater than or equal to 8, because this will help to ensure that participants will be diagnosed with MDD during session 1. Also, the stimulation is stratified based on SHAPS (>33 or ≤33). Thus, if 24 participants have completed either of the stratum, then participants within that stratum will not be eligible. In the case that a participant meets these criteria, there is still a chance that the first interview reveals that they do not meet study criteria. The study personnel completing the interviewing process will clearly explain why the participant does not meet criteria. However, in the case that a participant does not qualify based on suicide risk, procedures will be followed to ensure participant safety.

At the first session and after obtaining participant informed consent, the HAM-D will be administered, which contains a question related to suicidal thoughts/actions. If someone answers greater than 2 on the HAM-D (i.e., either "suicidal ideas or gesture" or "attempts at suicide") and indicates intent based on the C-SSRS, their participation in the study will be immediately stopped and [name] (Co-I, responsible for participant safety) will be contacted for acute assessment. In the case that the person does not see anyone for their depression, [name] will assist the participant in seeking medical care. [name] (Co-Investigator, mood disorders expert) will be available as well, in any instances where [name] is unavailable for acute assessment.

Assessment may include facilitating contact of the participant with their psychiatrist/primary care physician to establish a plan for safety, continued care, and follow-up. If the participant does not have an established provider, [name] will assist the participant in establishing care. If at any point in the assessment, the participant is deemed to be an imminent risk of harm to self or others, study personnel will Department for further care. In any instances where [name] is unavailable, [name] will be available to assist the participant. [name] will be the final arbitrator in case anything (e.g., eligibility, safety) is unclear during this process. [name] and the researcher will defer to [name] in those instances.

5.5 STRATEGIES FOR RECRUITMENT AND RETENTION

This clinical trial will utilize multiple recruitment strategies to communicate this opportunity to as many potential participants as possible. Our first means is through a referral process. Participants can be referred to the study through their primary mental health care provider or family doctor during routine visits. This type of recruitment will take place in and around Raleigh areas. We estimate that approximately 75 participants will be enrolled from the Chapel

Hill/Carrboro area and 25 between Durham and Raleigh. Clinicians will be informed of inclusion criteria through email and listserv announcements and be asked to mention this clinical trial to appropriate patients and offer them a flyer/ brochure with contact information. Interested individuals can then call or email the secure line/address to set up a phone prescreening. We will also be using the UNC i2b2 to send request forms to the Carolina Data Warehouse to recruit participants who have been seen at UNC Hospitals that meet the inclusion criteria.

In addition to referrals through primary care providers, we will advertise the study directly to the public on websites such as ClinicalTrials.gov, studypages.com, frohlichlab.org and Carolinaneurostimulation.org. We will have contact information and a summary of the clinical trial posted on the [name] Lab Facebook and Twitter pages. We may also be launching a Facebook ad to identify potential patients. This ad will also use a pre-screening survey via REDCap to help identify participants. We will also be using the UNC Mass email listserv to send out an email that has the studypages.com link. All patient identifiers will be stored in REDCap until recruitment is over. When recruitment is over, all patients who do not consent or are not eligible for participation in the study will have their responses permanently deleted in REDCap.

Retention is primarily achieved by condensing the bulk of the experiment into a single stimulation session. The payment is \$30 for completion of virtual clinical assessments session. Then, completion of the stimulation during task provides an addition \$50. Finally, participants are invited back for a third session that is an MRI session which provides \$40. Thus, completion of all study requirements gives \$120. However, completion of the in-person stimulation session is sufficient to address all primary and secondary outcomes. The participant will receive payment at the end of each session on a payment card that can be loaded. The research staff will also give each participant a reminder call or email for upcoming sessions. Each research staff member will be available for the participants to contact via email or phone.

6. STUDY INTERVENTION

6.1 STUDY INTERVENTION(S) ADMINISTRATION

6.1.1 STUDY INTERVENTION DESCRIPTION

Participants will be stimulated with the commercial, CE-certified NeuroConn Plus stimulator. The use of this device in this study has previously received a NSR designation on initial review by the full UNC IRB. The NeuroConn device description is as follows:

The DC-STIMULATOR is a CE-certified medical device for conducting non-invasive transcranial direct-current stimulation (tDCS) in humans. DC stimulation is used in clinical practice and in the research of stroke, epilepsy, migraine, tinnitus, depression, multiple sclerosis, dementia and chronic headache. The DC-STIMULATOR is a micro-processor-controlled constant current source. It meets the highest safety standards thanks to (hardware- and software-based) multistage monitoring of the current path. By continuously monitoring electrode impedance it can detect insufficient contact with the skin and automatically terminate stimulation, maximizing patient safety.

The device's alphanumeric display and the 4 touch keys allow various stimulation modes to be selected and stimulation parameters such as current strength, duration, fade-in and fade-out to be set.

DC-STIMULATOR features:

- 1 channel (anodal and cathodal stimulation possible)
- Adjustable current up to 5,000 μA *
- Adjustable application time up to 30 minutes *
- 2 standard modes - single (continuous stimulation) and - pulse (cyclical stimulation activation/deactivation) with fade in and fade out
- Customer-specific programs possible (optional)
- "Study mode" for blind processing of genuine and 'pseudo' stimulation (optional)
- External trigger input (optional)

6.1.2 DOSING AND ADMINISTRATION

The research team will first measure each participant's head using the 10-20 system to determine the electrode locations. Participants will then be fitted with the 3 electrodes for stimulation: two 4.5x4.5cm electrodes placed anterior and ventral to F3 and posterior and ventral to C3, and one 5x7cm electrode placed over FCz. Electrodes will be carbon rubber, with Ten20 conductive paste applied. During stimulation, the participant will be performing the EEfRT. The stimulator will be triggered by remote control from the experiment script and will administer stimulation for five-minutes during each of the 8 task blocks for a total of 40 minutes of stimulation. After each block of stimulation, an eyes-open resting state EEG will be performed. All stimulation involves 20 seconds of ramp-in time and 20 seconds of ramp-out time.

The stimulation waveforms used in this study for active sham stimulation (placebo) and for delta-beta and theta-gamma tACS are delivered at 1 mA zero-to-peak amplitude at the target electrodes and 2 mA zero to-peak amplitude at the return electrode. For active sham stimulation, the stimulation is left on for only 40 seconds before the stimulation ramps back out. This is intended to mimic the skin sensations (e.g., itching, burning, tingling) that are experienced at the onset of stimulation, assisting with blinding the participant's assignment.

Codes will be randomized to one of the three experimental arms. Researchers will enter the participant specific code into the MATLAB script that control the stimulator. Researchers will monitor participants during stimulation. Personnel will be thoroughly trained and have trainings documented on the transcranial stimulation device and will be present during all stimulation sessions. To monitor side effects of stimulation a stimulation effects questionnaire will be administered after each stimulation session.

6.3 MEASURES TO MINIMIZE BIAS: RANDOMIZATION AND BLINDING

Randomization

[name], a [name] Lab member, will oversee the randomization of 48 6-digit codes, which will be used by the experimenters. These codes are directly linked to which treatment participants receive

(sham/placebo or 10 Hz tACS at 1 mA) and will be entered into the MATLAB script. 24 codes are generated for each of the anhedonia stratum. In addition, 12 codes will be generated (6 extra codes for each stratum) in the event that a participant is randomized but discontinues the study. Thus, data will be collected until we reach our target of 48 participants, but there will be no bias towards completion for the different arms (in the unlikely event that one of the arms has more dropout than the others).

The assignment of each participant cannot be determined by looking at the codes (e.g., codes are not sequential, code assignment is not based on "odd/even" numbers). Thus, the study is both randomized and concealed by virtue of using random numbers generated by a computer. [name] has no other responsibility in the study other than providing these randomized codes. If [name] leaves the [name] Lab, another equivalent researcher who does not work with human participants will perform this task.

Blinding

This study is designed to be double-blind. This means that the participant and the researchers are unaware of each participant's assignment until the completion of all data collection. This is accomplished using the randomization codes described above. Furthermore, this study utilizes an active sham stimulation. This means that the active sham condition includes some stimulation, mimicking the skin sensations associated with tACS. In our previously concluded trial, participants in the delta-beta tACS, theta-gamma tACS, and active sham groups responded similarly to the blinding questionnaire, indicating that our active sham stimulation successfully blinded the participants.

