In the second session, participants provide written consent to participate in the study. Then, participants are randomized into one of three arms of the study: delta-beta tACS, control tACS in theta-gamma, or active sham. Randomization is stratified by SHAPS level such that there are an equal number of participants that are high anhedonia (SHAPS > 33) and low anhedonia (SHAPS ≤ 33). We expect that of the 48 participants in the final dataset, there will be 8 from each of the 6 groups (3 stimulation conditions by 2 anhedonia levels). Two 4.5 by 4.5 centimeters stimulation pads are applied to the scalp over the left hemisphere anterior and ventral to F3 and posterior and ventral to C3, and a 5 by 7 centimeters stimulation pad is applied centered over FCz in an anterior to posterior direction. Prior to any task performance, participants under eyes-closed and eyes-open resting-state while fixating on a central point on the monitor. Participants complete titration of the difficult of the EEfRT. Then, participants perform 4 blocks of the EEfRT during the collection of EEG. After each block of the EEfRT, there is a 2 minute eyes-open resting-state scan. Next, participants receive tACS during performance of the EEfRT. Delta-beta tACS, theta-gamma tACS, or sham-tACS is received during task performance. Stimulation is turned off between blocks, and eyes-open resting-state EEG is acquired. The total amount of stimulation is approximately 40 minutes for 8 blocks that

each last approximately 5 minutes. After tACS, participants complete a stimulation side effects questionnaire and a blinding questionnaire. A blinding questionnaire is completed by the experimenter. The blinding questionnaire is a single question that asks whether the participant receive stimulation or placebo, and then asks the participant to provide an explanation for their response. Based on the results of the stimulation side effects questionnaire, a structured adverse events interview is conducted to acquire more information regarding any side effects that were selected to be "very high" by the participant.

[figure not shown]

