4.2 SCIENTIFIC RATIONALE FOR STUDY DESIGN

This study is a double-blind, randomized, sham-controlled interventional study. The choice of double-blind and randomization is important for the integrity of our data, especially for the clinical assessments. All individuals involved with data collection (as well as all randomized participants) will be blind to the participant assignment until all data has been collected. This will reduce implicit and explicit bias in the data collection process. In this study, participants will be randomized in to one of three arms: active sham (i.e., placebo) stimulation, delta-beta tACS, or theta-gamma tACS. This is a follow-up to two of our previous studies. One study delivered this same form of stimulation in participants during a cognitive control task, which is different from the reward-based decision-making task described here. This study used a similar task design in which intermittent resting-state EEG found that delta-beta tACS and theta-gamma tACS increased the targeted neural activity and modulated behavior associated with the targeted neural activity. In this experiment, participants and researchers were successfully blinded to which stimulation condition they received. Furthermore, this previous study was a crossover design and, thus, a parallel arm design is even more likely to be double-blind because participants only receive one form of stimulation. A second study recorded EEG during the EEfRT in patients with MDD. This study found that participants with MDD and higher symptoms of anhedonia demonstrated reduced goal-directed behavior and reduced delta-beta coupling. This preliminary data provides strong evidence that stimulation delivered in a delta-beta pattern should be beneficial to behavioral performance. Furthermore, this study serves as a target engagement study and future studies may use these results to develop interventions to treat symptoms of anhedonia in MDD.

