9.4.7 PLANNED INTERIM ANALYSES

If there is an unexpected event that is related to tACS, then a blinded interim descriptive analyses on the safety measures (blinded adverse effects and responses to the stimulation questionnaire) will be performed. If there is a reason to review unblinded information, a researcher not involved in the data collection for the study, [name] or another researcher in the group, will be access the list of

participant identification numbers kept by [name]. Participant identification numbers will be in a table according to the two arms of the study; however, the treatment of each arm will not be disclosed. This information will allow the researcher to compare the two groups.

There are no other planned interim analyses.

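### The randomisation-code text (6.3) and the unblinded safety table (9.4.7) describe two arms, one of them a 10 Hz condition found nowhere else, in a three-arm trial

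*Combined protocol and SAP*

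**What the plan says.** Section 6.3 provides for 48 codes, 24 in each anhedonia stratum, plus 6 spare codes per stratum. It says that the codes determine the treatment received and names the treatments: "sham/placebo or 10 Hz tACS at 1 mA) and will be entered into the MATLAB script". It gives no allocation ratio and no number of codes per arm.

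Section 9.4.7 applies if an unexpected event is related to tACS and there is a reason to look at unblinded information: "Participant identification numbers will be in a table according to the two arms of the study". The identity of each arm stays masked, and the purpose is stated: "This information will allow the researcher to compare the two groups".

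Elsewhere the design has three arms:
- Section 4.1: "participants are randomized into one of three arms of the study: delta-beta tACS, control tACS in theta-gamma, or active sham". It expects that "there will be 8 from each of the 6 groups (3 stimulation conditions by 2 anhedonia levels").
- Section 4.2: "participants will be randomized in to one of three arms: active sham (i.e., placebo) stimulation, delta-beta tACS, or theta-gamma tACS".
- Section 4.3 lists the waveforms: "cross-frequency stimulation waveform delta-beta (3-20Hz), a control frequency of theta-gamma (5-50Hz), or sham".
- Section 6.1.2: "Codes will be randomized to one of the three experimental arms".
- Sections 9.1, 9.4.2, 9.4.3 and 9.4.5 all name the same three stimulation groups.

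**The concern.** Both conflicting passages are instructions. Section 6.3 is the dedicated text on producing the allocation codes, and the person who produces them has no other role in the study. Anyone working from that section alone would read a different trial from the one in 4.1. Section 9.4.7 governs the only unblinded look at safety data that the plan foresees before data collection ends.

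Two things are at stake. First, the protocol contradicts itself on what the codes stand for, and the number of codes would not alert anyone. Second, a two-column safety table cannot hold three arms unless two are merged or one is left out. If an adverse effect belonged to one waveform, the review meant to detect it could obscure it.

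**Working it through.** **1. Treatments attached to the codes.** Section 6.3 gives two: sham/placebo and a 10 Hz condition. Section 6.1.2 gives three. Section 4.3 describes only a 3-20 Hz waveform, a 5-50 Hz waveform, and a sham that uses one of these two briefly. No section other than 6.3 mentions 10 Hz. The 1 mA in the same parenthesis agrees with the target-electrode amplitude in 4.3 and 6.1.2, so it is not part of the contradiction.

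**2. Allocation arithmetic.** Inputs: 48 participants, 2 strata and 8 expected per cell (4.1); 24 main and 6 spare codes per stratum (6.3). Equal allocation is assumed. It matches the expectation in 4.1, but 6.3 does not state it.

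| Quantity | Three arms | Two arms |
|---|---|---|
| Participants per arm | 48/3 = 16 | 48/2 = 24 |
| Participants per arm-by-stratum cell | 48/(3×2) = 8 | 48/(2×2) = 12 |
| Main codes per arm per stratum | 24/3 = 8 | 24/2 = 12 |
| Spare codes per arm per stratum | 6/3 = 2 | 6/2 = 3 |

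The plan's own 8 per cell is reproduced with three arms only. Every code count is a whole number under both readings, so the counts alone cannot show which was used.

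**3. Does the sample size depend on this?** The caption of Figure 3 in 9.2 specifies 3 groups, 2 measurements, an effect of 0.288 and a correlation of 0.5; the text states 93% power with 48 participants. For the within-between interaction, λ = f²·N·m/(1 − ρ). Entering 0.288 directly as f gives λ = 0.288² × 48 × 2/0.5 = 15.9. At a two-sided threshold of 0.05:
- three groups (2 and 45 degrees of freedom): power 94.2%;
- two groups (1 and 46 degrees of freedom): power 97.4%.

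The stated figure is close to the three-group value. This check separates the two readings only when 0.288 is taken as f. Converted from partial eta-squared, f = √(0.288/0.712) = 0.636 and power is about 100% for either number of groups. That conversion is a separate matter, as is the running text of 9.2, which names only delta-beta and placebo as levels.

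**4. The two-column safety table.** Let the event rate be s under sham and in the unaffected active arm, and s + d in the affected active arm, with n participants in each active arm. Pooling the active arms gives [n(s + d) + n·s]/(2n) = s + d/2, so the excess over sham is halved. If the affected arm is the one omitted, the excess is not seen at all. At full enrolment the pooled layout would also have columns of 32 and 16, so column size would identify sham although 9.4.7 says that the arms stay masked.

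**The case against.** The case on the other side is that this is leftover wording that nobody could act on. Much of that stands. Section 6.1.2 names the three stimulation types and then ties the codes to three arms, so 6.3 is not the only statement of the link. A 10 Hz condition could not be delivered from this protocol because no such waveform is described. The same paragraph of 6.3 speaks of one arm having more dropout than the others, a plural that suits more than two arms.

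A reader might therefore infer too much from 6.3, namely that following it yields a 1:1 two-arm list and loses the theta-gamma arm. The documents do not support that. Section 6.3 gives no ratio, and the three-arm design is stated consistently almost everywhere else. The 12 per arm per stratum above is an arithmetic comparison, not a predicted outcome.

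On safety, a reader might infer that the trial could not detect a waveform-specific effect. That also goes too far. Section 9.4.5 compares each active arm with sham separately and models all three groups, and 10.1.6 provides for adverse events to be reviewed as they occur. The table in 9.4.7 comes into play only after a triggering event and a blinded first look.

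The objection does not remove the contradiction. Two sections disagree about what the same codes mean, and the table in 9.4.7 cannot be built for three arms as worded.

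**Conclusion.** The inconsistency is real and should be corrected. Sections 6.3 and 9.4.7 are wrong for a three-arm trial; 6.3 conflicts with 6.1.2 about the same codes, and 9.4.7 does not match the separate active-versus-sham comparisons in 9.4.5. The sample size and the primary, secondary and final safety analyses are built on three groups and do not change.

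The more tangible consequence lies in 9.4.7. If the active arms were pooled, an excess confined to one of them would be halved; this assumes equal active arms and no excess in the other. It is limited to a contingent review that may never take place. For 6.3 the risk is confusion when the code list is made or checked. The documents do not show that a wrong list exists, or that any list had been made when the text was written.

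**What to change.** - **Section 6.3:** reconcile the treatment list with the three arms named in 4.1 and 6.1.2. This concerns the number and identity of the arms only; no stimulation setting is proposed here.
- **Section 6.3:** state the number of codes per arm in each SHAPS stratum, consistent with the expected 8 per cell (8 + 8 + 8 = 24). An even split of the 6 spare codes, 2 per arm, is optional; the documents do not require it.
- **Section 9.4.7:** provide a table with three masked columns and a comparison of all three groups, in line with 9.4.5.
- **Code list:** if one has already been generated, someone outside data collection should check that it contains the three arms in the intended numbers within each stratum.

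The cost is a few lines of protocol wording and one check of a list. No analysis or sample size has to be redone.
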